14.0 Withdrawal of Subjects*

- 14.1 Infant participants may be withdrawn from the study if they become ineligible for participation based on the inclusion and exclusion criteria between the time that written informed consent is obtained from parents and the time that data collection commences. Nurse participants will not be withdrawn from the study.
- 14.2 If infants are withdrawn from the study prior to data collection, we will inform parents that their infant is no longer participating in the study due to pre-established inclusion and exclusion criteria.
- 14.3 If infants are withdrawn from the study, previously collected data (i.e. demographic data) may be used but further data collection will cease.

15.0 Risks to Subjects*

15.1 ***Infant risks.*** We do not expect the static touches provided during the NaTI to increase the risk for physiologic decompensation beyond the risk that exists for essential nursing care. We expect that infants will experience physiologic regulation during these touches. However, the NaTI will extend the duration of the care episode by 2.5 minutes. Some studies of massage in preterm infants report no adverse events related to the intervention⁹⁶⁻⁹⁸. A few investigators have reported infrequent occurrences of bradycardia, apnea, or desaturation associated with massage^{99,100}. In a study of tactile stimulation in preterm infants 26-32 weeks PMA, Fucile and Gisel (2010) paused the intervention for 1.1% of the administrations due to bradycardia, apnea, or oxygen desaturation. While these are possible risks in our study, we expect the occurrence of bradycardia, apnea, and oxygen desaturation to be infrequent, especially given the static nature of the NaTI in contrast to the stimulation of massage or tactile stimulation.

We will collect biobehavioral data from infants. HR and HRV will be collected from monitoring equipment similar to that used as part of clinical care in the NICU. The collection of HR and HRV data will require the attachment of three additional ECG electrodes to the infant's chest. If the infant's chest is not large enough to accommodate the additional electrodes, electrodes for clinical monitoring can be moved to the infant's back at the nurse's discretion. The additional ECG electrodes may cause mild erythema after removal, similar to the removal of electrodes used for clinical monitoring. SCRs will require the attachment of two additional electrodes with isotonic gel to the infant's foot. These electrodes may cause mild erythema after removal, similar to the removal of electrocardiogram electrodes used for clinical monitoring. Salivary cortisol will be collected three times during the observation period (prior to the start of the care episode, 30 minutes after the care episode, 60 minutes after the care episode) using small medical swabs similar to those used to provide oral care to preterm infants. The swab will be gently introduced into the infant's mouth and held securely using the attached handle. There are no expected risks to infants from the saliva collection. Protected health information (PHI), including maternal prenatal data and infant clinical data, will be collected from each infant's EHR. There is a small risk of loss of confidentiality.

Nurse participants. Nurses will be asked to complete a demographic questionnaire once and an investigator-developed NaTI survey, the AIM⁹⁰, the IAM⁹⁰, and the FIM⁹⁰ each time they provide the NaTI to an infant. There is a small risk of loss of confidentiality for nurses who agree to participate. Surveys request nurse feedback on the intervention and will not include sensitive data.

- 15.2 As part of the biobehavioral data collection, there may be risks to infant participants that are not foreseeable.
- 15.3 If a pregnant nurse chooses to participant in the nursing survey study, there are no risks to her fetus.

16.0 Potential Benefits to Subjects*

- 16.1 Infants may directly benefit from the comforting touches provided by the NaTI although we can neither offer nor guarantee this potential benefit. We hypothesize that these touches will attenuate activation of the infant's stress response systems.

16.2 There is no direct benefit to nurses who participate in the nursing survey study. The survey study provides nurses with the opportunity to describe their perception of the NaTI and their suggestions for NaTI revisions. In this way, nurses will have the opportunity to be part of the decision-making process for their practice.

17.0 Data Management* and Confidentiality

17.1 **Aim 1.** The primary aim is to determine the effect of a NaTI on biobehavioral stress responses of preterm infants during essential nursing care. Our primary analysis will compare mean values of biobehavioral stress responses during an episode of essential care between cohorts (comparison vs interventions conditions). We will begin by examining sequence effects. We will then compare the biobehavioral stress responses of infants assigned to each condition using linear mixed models to account for multiple observations within infants. Additional variables may be added if potential confounding variables are identified between conditions, although none are anticipated. Secondary analyses will consider total area under the curve (AUC) for each biobehavioral response variable to identify important differences in overall recovery between conditions. For the primary (i.e. comparison of means during care) and secondary (i.e. comparisons of AUC) analyses, we will examine differences in outcomes by important biological variables (e.g. infant sex) and will repeat the analysis, including interactions to identify possible moderation of the effect by infant sex, race, ethnicity, and PMA at birth.

Aim 2. We will use measures of central tendency and variance to describe nurses' Likert responses. We will identify barriers and facilitators of intervention implementation for each episode of essential care during hospitalization from narrative responses.

Aim 3. We will use correlation analysis and regression models to determine the associations between biobehavioral stress responses and neurobehavioral outcomes.

17.2 To protect the confidentiality of infant and nurse participants and their data, infant and nurse participants will be assigned a SID that will be used to label all data and samples. No other identifying information will be included on data forms. The key linking identifying information and SIDs will be encrypted and stored on an electronic password-protected research server at the OSU CON. The key linking names and SIDs, electronic and paper data forms, and consent forms will be stored in separate locations. Electronic access to the research server is restricted to the OSU CON local area network or virtual private network by a Cisco ASA 5510 firewall. Paper data forms and consent forms will be stored in locked filing cabinets in a locked office at the OSU CON. Access to the key, data, and consent forms will be limited to research team members who have been approved by the IRB and are compliant with all required training in the protection of human subjects.

17.3 We will verify 100% of the data collected from the EHR for 25% of infant participants against the source documentation (i.e. EPIC).

17.4 All data and samples will be transported to the OSU CON under a Data Transport Authorization from the NCH Privacy Office and stored at the OSU CON under Data Use and Materials Transfer Agreements. With parental consent for infant data

and samples and nurse consent for nurse data, data and samples will be stored indefinitely. Access to the data and samples will be limited to study staff who have been approved by the IRB, are compliant with human subjects protections training, and have been trained by the PI on data storage procedures. Data and samples will be transported only by the study PI.

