6.0 Procedures Involved*

PROTOCOL TITLE: Pilot Study of Nurse-Administered Touch and Biobehavioral Stress Responses of Preterm Infants (Pilot NAT-BIO Study)

6.1 **Study Design. Aim 1.** Infants will be assigned to standard care or standard care with the addition of the NaTI in a randomized cross-over manner to determine the effect of a NaTI on biobehavioral stress responses during essential nursing care. We define essential nursing care as a scheduled episode of clustered caregiving activities related to health monitoring, hygiene, and clinical needs that includes at least a diaper change and feeding. We will enroll up to 20 infants for this pilot study to collect complete, usable data on 16 infants.

Aim 2. To identify factors to increase the feasibility of the NaTI as a nurse-administered, integrated part of essential, procedural care, we will conduct a survey study of nurses who have provided the NaTI to enrolled infants. We will specifically ask nurses to describe barriers and facilitators of implementation.

Aim 3. We will use a longitudinal cohort design to determine associations between biobehavioral responses and early neurobehavior. We will collect biobehavioral stress response data during the two observed episodes of care and will administer the NAPI to each enrolled infant at approximately 35 weeks PMA.

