6.2 **Procedures. Aims 1.** Infants will be enrolled during the first 10 days of life. We will collect demographic and clinical data from the infant's electronic health record (**EHR**) after enrollment and throughout the hospitalization. Because stress responses may differ based on postnatal age⁸¹, data collection for stress responses will occur between 10 and 20 days of life. To eliminate variance in cortisol due to diurnal patterns, we will perform all observations at the same time of day for all infants, between 1000 and 1300. Observations will occur on two consecutive days unless infants are not available due to off-unit or other scheduled procedures. In this case, the second observation will occur on the next day that the infant is available. Infants will be assigned to receive standard care or standard care with a NaTI in a randomly assigned sequence. For the two observed care episodes, we will require that nurses provide this care exclusively to limit confounding by the participation of additional caregivers. With assistance from the bedside nurse, the researcher, who is a Registered Nurse, will attach monitoring electrodes for vital signs, HRV, and SCRs during the care episode prior to the observed care to minimize stress responses from handling and monitoring prior to the baseline period (Fig 2). Nurses commonly attach monitoring electrodes as part of their clinical practice.

[figure not shown]

Figure 2. Timeline of study measures.

Measures, Aims 1:

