- **SAM pathway activation.** Heart rate will be measured continuously during the observed care episode, using external monitors. HR, a measure of SNS response, is our primary outcome measure because nurses can use HR in clinical practice to identify SAM pathway activation. Heart rate variability, specifically high frequency HRV (**HF HRV**), provides an index of PNS activity and is generally reduced in response to internal or external stressors⁸². Continuous electrocardiogram (**ECG**) data during baseline, care episode, and recovery will be collected using external Holter monitors. Electrodes for ECG data will be applied by the researcher with assistance from the bedside nurse during the care prior to each observed care. Raw ECG waveform data will be imported into Co-I [name]'s MARS® Ambulatory ECG Analysis and Editing System (General Electric, Inc.) and processed according to recommended protocols^{82,83}. During processing, artifact will be eliminated with final calculations based on normal sinoatrial node-initiated complexes. Analysis will include HF HRV calculated in one-minute epochs averaged for each phase (i.e. baseline, care episode, recovery). Skin conductance responses will be measured by attaching two disposable electrodes with isotonic electrode gel (Biopac Systems, Goleta, CA) to one foot approximately three hours prior to data collection (i.e. during the episode of care prior to the observed episode of care). Electrodes are connected to an amplifier to record SCRs during the entire observed care. At the beginning and end of each period (baseline, care episode, recovery), we will record ambient (i.e. room or incubator) and infant skin temperatures; ambient and skin temperatures <24°C and <32°C, respectively, may affect SCRs^{84,85}.

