Co-I [name] (OSU) will provide all statistical support for the project. [name] will develop the randomization scheme for the cross-over trial and will assist in addressing data collection issues related to missing data or other unforeseen circumstances. [name] will conduct the statistical analysis to address the aims. [name] will participate in interpretation of study findings and dissemination efforts.

Co-[name] (NCH) will serve as site PI for NCH and will act as liaison between OSU and NCH, assisting with the identification and recruitment of participants at the clinical site. [name] will ensure the safety of all study participants and will assist with reviewing and reporting adverse events, as required. [name] will assist with data interpretation and dissemination efforts.

Graduate Research Assistants will be hired to assist the PI in completing the day-to-day operations of the study, including on-site data collection, cleaning and analysis of physiologic data in preparation for statistical analysis, and data entry. The Research Assistants will perform HRV analysis under the supervision of the PI.

- 25.3 All members of the study team will be required to complete and maintain current CITI Program training as required by NCH and OSU. PI [name] will train all study staff on relevant standard operating procedures relevant to each person's assigned responsibilities and will document this training in study records.
- 25.4 All equipment and supplies need to perform study activities are available at NCH or OSU or will be purchased from the study budget.

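### The primary crossover model names no period (day) term, and its sequence check has neither a definition nor a consequence

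*Combined protocol and SAP*

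**What the plan says.** Section 17.1 (Aim 1) holds the primary model, a contrast of mean responses during care between conditions. It starts with a check: "We will begin by examining sequence effects". No test, level or follow-up action is attached. The investigators will then "compare the biobehavioral stress responses of infants assigned to each condition using linear mixed models to account for multiple observations within infants". Neither day nor a pre-care baseline is listed as a term. Other terms can enter by one route only: "Additional variables may be added if potential confounding variables are identified between conditions, although none are anticipated".

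Section 6.2 also contains analysis statements: averaging of HF HRV by phase, and use of the context-of-care data. None of them adds a period term to the primary contrast.

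The design facts that bear on this are:

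- **Timing (Section 6.2).** Sequence is assigned at random and the two observations normally fall on consecutive days. If an infant is unavailable, "the second observation will occur on the next day that the infant is available". Age is restricted: "data collection for stress responses will occur between 10 and 20 days of life". Time of day is held constant.
- **Numbers (Section 6.1).** "We will enroll up to 20 infants for this pilot study to collect complete, usable data on 16 infants".
- **Allocation (Section 25.2).** A co-investigator "will develop the randomization scheme for the cross-over trial". No ratio or blocking is given.
- **Measures (Sections 6.2 and 15.1).** For the primary outcome, "Heart rate will be measured continuously during the observed care episode, using external monitors"; the Holter ECG also covers the baseline. Cortisol is sampled before care and 30 and 60 minutes after it, never during it.

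**The concern.** In a two-condition, two-day crossover, every infant's condition difference is also a day difference, with a sign set by sequence. If responses differ systematically between day 1 and day 2, a model without period must put that difference somewhere. With equal sequences it goes into the error term. With unequal sequences part of it also goes into the condition estimate.

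The two existing provisions do not close this gap. The covariate clause is optional and depends on finding a confounder. At 8:8, day is not confounded with condition, so the clause would not be triggered, yet that is where power is lost. The sequence check could mean carry-over, or it could mean order, which in this design is the period effect. Under either reading the plan does not say what follows.

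At stake is the precision of the preliminary effect estimate, and its accuracy given the split that actually occurs. That estimate is a main product of a pilot.

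**Working it through.** **No plan figure to reproduce.** The documents give no alpha, power, SD, target effect, day shift or correlation. All of these are assumptions here.

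**Inputs.** From the documents: 16 complete pairs, two conditions, two days. Assumed: one care mean per infant per day, two-sided 5% level, and an effect of 0.75. The unit is the SD of the within-infant difference (NaTI minus standard care). The 0.75 was chosen because it gives about 80% power.

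**Model.** D = tau + s·g + e, with SD(e) = 1. Here s is the day 2 minus day 1 shift, and g = +1 if NaTI falls on day 2 and −1 if on day 1. On complete pairs, the condition-only random-intercept model is a paired t test (15 df). Adding period compares D between sequences and averages the two sequence means (14 df).

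**Equal split, 8:8.** There is no bias. The expected residual variance without period is 1 + s²·16/15. For s = 0.5 this is 1 + 0.25 × 1.067 = 1.267, so the reported standard error is √1.267 = 1.13 times too large. Simulated power without period is 78% (s = 0.25) and 72% (s = 0.5), against 80% with period.

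**Unequal splits.** Given the split, the shift in the estimate is s·(n1 − n2)/16. For s = 0.5 at 10:6 it is 0.5 × 4/16 = 0.125. Adding period multiplies the variance by N²/(4·n1·n2); at 10:6 that is 256/240 = 1.067.

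| Split | Shift in estimate, s = 0.25 | Shift in estimate, s = 0.5 | Type I without period, s = 0.5 | Variance factor with period | Power with period |
|---|---|---|---|---|---|
| 8:8 | 0 | 0 | 3.0% | 1.000 | 80% |
| 9:7 | 0.03 | 0.06 | 3.4% | 1.016 | 79% |
| 10:6 | 0.06 | 0.125 | 4.9% | 1.067 | 77% |
| 11:5 | 0.09 | 0.19 | 7.5% | 1.164 | 74% |
| 12:4 | 0.125 | 0.25 | 11.7% | 1.333 | 68% |

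With period in the model the estimate is unbiased and type I error is about 5% in every row. Without period and with no day shift, power is about 80% in every row.

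**How likely are unequal splits?** The scheme is not given, so two cases are shown.

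- Simple randomisation of 16: P(unequal) = 1 − 12870/65536 = 0.80, and P(11:5 or worse) = 13770/65536 = 0.21. Averaged over all splits, type I error at s = 0.5 is 5.0%.
- 10:10 with 4 lost at random: P(8:8) = 45²/4845 = 2025/4845 = 0.42, so 58% of trials are unequal, none worse than 10:6.

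**Mean squared error.** Relative to 1/16, it is 1 + s²(n1 − n2)²/16 without period. Setting this equal to the variance factor gives s = √(0.0159 × 4) = 0.25 at 9:7 and s = √0.0667 = 0.26 at 10:6. Below that shift, leaving period out is slightly better.

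**Can the sequence check stand in for a period term?** At 8:8, 14 df and the 5% level:

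- Read as order, the noncentrality is s/0.25 = 4s. Power is 15% for s = 0.25 and 46% for s = 0.5.
- Read as carry-over of 0.75, it is 0.75·√((1 − ρ)/(1 + ρ))/√(2/8), where ρ is the within-infant correlation. Power is 18% at ρ = 0.3 and 8% at ρ = 0.8.

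**Baseline, added to period at 8:8.** The variance factor is (1 − r²)·13/12, where r is the correlation between the two-day baseline difference and the two-day care difference. Break-even is r = √(1/13) = 0.28. Power is about 76% at r = 0, 80% at 0.3 and 87% at 0.5.

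**The case against.** The strongest reply is that sequence is randomised. If losses are unrelated to sequence, the condition-only contrast is unbiased over repeated allocation, and the displacement at a given split is chance imbalance. That stands. A reader might infer that the planned estimate is biased outright, and the documents do not support that. The trial will still be analysed at one realised split, and a period term removes the displacement there.

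A second reply is that no harm is demonstrated. The statement in Section 6.2 that responses may vary with postnatal age might be read as evidence of a day effect. It explains the age window and does not show a shift over one day. The sizes are also modest: 0.06 at 9:7 is a quarter of the 0.25 standard error. Averaged over the 10:10-lose-4 splits, relative mean squared error at a 0.25 shift is 1.013 without period and 1.014 with it. At 0.5 it is 1.053 against 1.014. This limits the severity but does not remove the point.

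A third reply is that order is partly handled, since a sequence check comes first and terms may be added. That is fair. The gap is in definition and pre-specification. Nor does the text say that a positive check would lead to a day-1-only analysis, so error inflation from such a two-stage procedure cannot be charged to the plan.

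**Conclusion.** The point holds as a should-fix. As written, the primary model is condition-only for a two-day crossover, and neither the sequence check nor the covariate clause secures a period term.

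If the days differ, the cost is lost power at equal sequences (80% to 72% for a 0.5 SD shift). At unequal ones it is a conditional displacement of (n1 − n2)/N of the shift. Two flat statements about type I error would both be wrong. Omission does not inflate it in general: at a 0.5 shift it is 5% or lower up to 10:6, and 5.0% averaged over simple randomisation. It is inflated at splits of 11:5 or worse, which simple randomisation of 16 would produce 21% of the time.

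Nothing here makes the trial invalid, and nothing shows that baseline adjustment is needed. Every magnitude rests on assumed shifts, an assumed effect and 16 complete pairs. The effect of a variable gap between the two days was not quantified.

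**What to change.** **Core change (wording in Section 17.1).** Pre-specify the primary model as mean during care on condition + period (day 1 or 2) + sequence, with a random infant effect and small-sample (for example Kenward-Roger) degrees of freedom. Define the sequence check, report it descriptively, and state that it will not alter the primary analysis. For cortisol, name the outcome time point, because a mean during care does not exist for it.

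**Cost.** No new data are needed. The term uses one degree of freedom and adds 0%, 1.6% or 6.7% variance at 8:8, 9:7 or 10:6. With no day effect, power goes from about 80% to 80%, 79% or 77%. The price is higher at more extreme splits (16% more variance at 11:5 and 33% at 12:4). At 9:7 and 10:6 the term pays for itself in mean squared error only from a day shift of about 0.25 SD. A day 1/2 term does not model a postponed second day.

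**Optional and secondary.** Pre-specify a supportive analysis, in infants observed on both days, that adds the same-day pre-care baseline as a covariate and not as a change score. For HR, derive it from the baseline Holter ECG over a defined window. It helps only if r exceeds about 0.3. It also assumes that the day-1 condition does not carry over into the day-2 baseline: a 0.25 SD shift of that baseline alone would bias the adjusted contrast by 0.04 to 0.09 SD (r = 0.3 to 0.7).

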5.0 Study Intervention/Investigational Agent

- 5.1 Description. The NaTI is a systematic touch intervention consisting of three static, brief touches provided by bedside nurses at specified points during essential care. To provide the NaTI, nurses will cradle the top of the infant's head with one hand, using their other hand to contain the infant's lower body. Nurses will provide the touch for one minute at the start of the care to allow infants time to acclimate to the stimulation, 30 seconds after the diaper change, and one minute at the conclusion of the care to provide a gradual end to the care and facilitate infant recovery and sleep. Nurses will provide the touches using bare hands (i.e. no gloves) to provide infants with human skin-to-skin contact and will perform hand hygiene before and after each touch. Nurses often provide discretionary comforting touch, commonly referred to as hand containment or facilitated tucking, in the same manner as the NaTI as part of their routine care (NCH Patient/Family Care Policy 30:23). The NaTI differs from discretionary comforting touch in that it is provided at specific points during the care and for a prescribed length of time. A member of the research team will be present during the care, perform timing for the intervention, and provide verbal instructions for nurses to begin and end the NaTI.

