- **HPA axis activation.** Salivary cortisol will be measured from saliva samples taken immediately prior to the start of care (baseline), 30 minutes after the care has ended (post-care), and 60 minutes after the care has ended (recovery; Fig 2) using medical sponges gently introduced into the infant's mouth.. We have previously used these sponges for saliva collection from preterm infants without causing infant distress. A member of the research team, who is a Registered Nurse, will collect saliva samples with the assistance of the bedside nurse. Saliva collection is non-invasive and may be collected as part of clinical practice (test code XSCRT according to the NCH Laboratory Medicine website; see protocol Appendix). We will batch process samples and quantify cortisol levels using a commercially available enzyme-linked immunosorbent assay (**ELISA**; Salimetrics, State College, PA).
- **Recovery.** We will measure infant recovery by recording episodes of bradycardia, tachycardia, oxygen desaturation, or other monitor alarms during the 30-minute recovery period following the episode of essential nursing care. We will observe sleep behaviors to determine if the infant is awake, asleep, or drowsy during this 30-minutes recovery period using the Anderson Behavioral State Scale (ABBS). Behavioral data will be collected through observation without disturbing or handling the infant.
- **Context of care.** We will record the duration of the caregiving episode and the procedures included. We will use the acute scale of the Neonatal Infant Stressor Scale (**NISS**)⁸⁸ to quantify the procedural stressors experienced by infants during the observed care episode. We have previously modified this measure to account for

the procedural stressors commonly experienced by preterm infants⁷⁷. Additionally, we will observe and record all direct touches experienced by the infant for one hour prior to the caregiving episode. Direct touches are those defined as direct physical contact between a caregiver and infant and might include parent skin-to-skin care, interventions for apneic episodes, and adjustment of a respiratory interface. We will use these data to compare the context of care for infants between assigned conditions and will examine moderation of infant responses to care episodes by this context.

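### The open covariate clause in Section 17.1 can admit care duration, which the NaTI itself lengthens by 2.5 minutes, into the primary model

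*Combined protocol and SAP*

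**What the plan says.** Section 17.1 (Aim 1) compares mean responses during care between NaTI and standard care. It looks at sequence effects first and then fits linear mixed models. Heart rate is the primary outcome (Section 6.2). On covariates, Section 17.1 adds: "Additional variables may be added if potential confounding variables are identified between conditions, although none are anticipated". It names no candidates, sets no criterion for a difference, and does not restrict candidates to variables fixed before the care episode starts.

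Under context of care, Section 6.2 states: "We will record the duration of the caregiving episode and the procedures included". It also records NISS stressors during the observed episode and direct touches in the hour before it. The stated use is to "compare the context of care for infants between assigned conditions and will examine moderation of infant responses to care episodes by this context".

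Section 15.1 says that "the NaTI will extend the duration of the care episode by 2.5 minutes".

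The interaction analyses in Section 17.1 concern "possible moderation of the effect by infant sex, race, ethnicity, and PMA at birth". Care context is not on that list.

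**The concern.** A variable that the assigned condition changes is not a confounder of that condition's effect. Care duration, in-care procedures and in-care NISS stressors all arise after assignment, and the protocol itself says that duration will be longer under the NaTI. A clause that opens the primary model to variables found to differ between conditions, with no pre-care limit, leaves room for one of these to be added.

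Two things are at stake. First, adjusting for duration changes the question from the effect of adding the NaTI to care as delivered to a contrast at equal episode length. Second, choosing covariates after seeing imbalance in about 16 infants leaves the primary estimate open to selection.

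The planned moderation by context raises a separate problem of interpretation: for duration and in-care procedures, the moderator is itself affected by treatment.

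**Working it through.** **1. The plan's own figure.** Section 5.1 specifies "one minute at the start of the care to allow infants time to acclimate to the stimulation, 30 seconds after the diaper change", and a further minute at the end of care. The sum is 1 + 0.5 + 1 = 2.5 minutes, which reproduces Section 15.1.

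**2. What the clause can act on.** For an infant observed under both conditions, a fixed trait (sex, PMA at birth, SNAP-II) has a within-infant difference of exactly zero. Among the planned 16 complete infants, only variables that change from day to day can differ between conditions. The set that Section 6.2 says will be compared is care context. Within it, touches in the prior hour precede care; duration, procedures and NISS stressors do not.

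**3. Shift if duration is added.** Let Y be an infant's difference in mean heart rate (NaTI minus standard care), D the difference in care duration (mean 2.5 min), τ the total effect, and b the within-infant slope of heart rate on duration. Leaving out the period term:

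Y = τ + b(D − 2.5) + error = (τ − 2.5b) + bD + error

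With D in the model, the treatment coefficient estimates τ − 2.5b instead of τ. The documents give no b, so the range is an assumption:

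- b = 0: shift 0
- b = 0.5 bpm/min: −1.25 bpm
- b = 1: −2.5 bpm
- b = 2: −5 bpm

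A positive slope makes the NaTI look more favourable. A simulation agrees (n = 16, period term, 6,000 runs per scenario; assumed τ = −5 bpm, residual SD 8 bpm, SD of D 5 min). Adjusted means were −5.00, −6.26, −7.48 and −9.94 bpm for the four slopes; unadjusted means stayed between −4.93 and −5.00.

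The slope need not be causal. A third factor, such as a fussy infant, could both lengthen care and raise heart rate. Also, Sections 4.2 and 6.3 stop a touch on heart-rate or saturation criteria, so duration under the NaTI may depend partly on the primary outcome.

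**4. Precision.** If duration does not predict heart rate (b = 0), the standard error is multiplied by about √(1 + n × 2.5² / ((n − 1)s²)), where s is the SD of D (assumed). With n = 16:

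- s = 2.5: √(1 + 100/93.75) = 1.44
- s = 5: √(1 + 100/375) = 1.13
- s = 10: √(1 + 100/1500) = 1.03

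The simulation also fits a period term and lets the mean and SD of D vary between runs. Its ratios of adjusted to unadjusted standard error are:

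| s (min) | b = 0 | b = 0.5 | b = 1 | b = 2 |
|---|---|---|---|---|
| 2.5 | 1.52 | 1.54 | 1.46 | 1.30 |
| 5 | 1.19 | 1.12 | 1.01 | 0.75 |
| 10 | 1.08 | 0.93 | 0.68 | 0.40 |

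Precision can go either way.

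**5. How readily duration would be flagged.** The plan states no test. If a 5% paired t-test were used with n = 16, the noncentrality would be 2.5 × √16 / s = 10/s on 15 degrees of freedom. The chance of flagging is 0.962, 0.465, 0.239 or 0.155 for s = 2.5, 5, 7.5 or 10 min.

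**6. Moderation.** Section 6.2 says the team "will examine moderation of infant responses to care episodes by this context". Section 17.1 lists sex, race, ethnicity and PMA at birth only. The two do not match, and Section 6.2 does not separate pre-care from in-care context.

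**The case against.** The strongest reply is that the clause is discretionary and asks for potential confounding, not mere difference. Properly read, a consequence of treatment does not qualify. No section names duration as a covariate. The team may expect 2.5 extra minutes and still expect no confounders, so Sections 15.1 and 17.1 can both be true. Section 3.1 also promises blinded analysts, and this is a pilot of up to 20 infants.

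Much of this stands. A reader might infer that the clause will bring duration in, or that the protocol contradicts itself. The text supports neither: it says *may*, and even a significance trigger would fire with a chance that depends heavily on an unknown SD. A reader might also infer that the contrast is necessarily less precise; the table in the working shows that this is not general. Nor can a supplementary moderation analysis bias a separately fitted primary contrast.

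What the reply leaves untouched is that nothing excludes duration, and that care context is the main set of variables on which the clause can act. Section 3.1 attributes bias in earlier trials partly to unmeasured contextual factors, so treating context as confounding would be a natural step for this team. Blinding the analyst limits choice by direction of effect, but it does not stop a post-assignment variable being selected. Where precision improves, it improves for a different contrast.

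**Conclusion.** The concern holds as a gap in the specification with a foreseeable wrong use. Section 17.1 allows data-driven covariates in the primary model without a pre-care limit, and one variable that the team will compare is lengthened by the intervention itself.

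The documents do not show that the primary contrast is biased. That requires duration to enter the model and to be related to heart rate within infants. Under those conditions the shift is 2.5 bpm per 1 bpm/min of slope. The slope, the SD of the duration difference and the residual SD are all assumptions, so the size cannot be fixed from the documents.

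Separately, the moderation plan in Section 6.2 does not match Section 17.1. For duration and in-care procedures, an interaction with condition would be hard to interpret.

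**What to change.** - Replace the covariate sentence in Section 17.1 with a primary model fixed in advance: condition, period, sequence and the same-day pre-care value of the outcome. Direct touches in the hour before care may be listed as an optional further term, provided the decision is made before the data are seen.
- State that duration, procedures and NISS stressors during care will not be covariates in the primary model. Report them by condition, descriptively or in a labelled sensitivity or mediation analysis.
- Limit context moderators to variables measured before care starts, and make Section 6.2 and the moderator list in Section 17.1 agree.

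The cost is wording in two sections. No new infants or measurements are needed, since Section 6.2 already collects baseline ECG and a pre-care saliva sample. The team gives up post hoc covariate choice. With 16 within-infant differences, condition and period leave 16 − 2 = 14 degrees of freedom; the baseline term leaves 13, and prior-hour touches would leave 12.
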